We are proposing a double-blind, placebo-controlled study that enrolls young adult smokers stratified for menthol preference. Menthol and control flavor will be delivered via an e-cigarette just prior to saline or IV nicotine infusion. This menthol / nicotine reinforcement study was preceded by a separate menthol dose-finding study that determined the low and high doses of menthol to be administered by the e-

[Type text]

[Type text]

cigarette. For this dose-finding study, subjects were screened at the West Haven site where the IV nicotine study will be performed, but the dose-finding study was conducted at the John Pierce Labs located on the Yale Campus located about 2 miles from the West Haven site. The screening procedure for the dose-finding study was described in a separate screening consent form. The dose-finding study did not administer any nicotine.

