For this menthol / nicotine reinforcement study, the Test Sessions will be conducted after an Adaptation Session is completed where subjects will learn to use the e-cigarette for delivering the menthol or control (tobacco) flavor. A short e-cigarette questionnaire will also be administered during the Adaptation Session. Then, the nicotine Test Sessions will be performed following overnight abstinence from tobacco. Smokers will be assigned a random sequence of three different e-cigarette conditions (low menthol (0.5% or 5 mg/mL) plus tobacco flavor, high dose menthol (3.5% or 35 mg/mL) plus tobacco flavor or tobacco flavor alone for each of the three Test Sessions (a different menthol condition for each session). The concentration of tobacco flavor will be identical across all conditions. The amount of menthol in high dose condition is the same as those found in commercially available mentholated e-cigarette solutions (AmericaneLiquidStore™). The low dose menthol solution contains menthol that is minimally perceptible by smokers and is in the range of e-cigarette solutions targeting smokers with a preference for low menthol impact in the e-cigarette vapor. In each Test Session, smokers will receive a random order of one intravenous delivery of saline, and two intravenous deliveries of nicotine (3.6 mcg/kg and 7 mcg/kg or 0.25 mg/70 kg and 0.5 mg/70kg), just after the menthol or control flavor is delivered via the e-cigarette. The intravenous dose deliveries will be one hour apart to provide sufficient time for the nicotine and menthol effects to wear off. The nicotine infusion sessions will be at least 24 hours apart to minimize carryover nicotine effects. The main outcome measure will be subjective drug effects as measured with the Drug Effects Questionnaire (DEQ). Other outcomes include cardiovascular measures, cognitive performance, and self-report measures of nicotine withdrawal. Cardiovascular measures include heart rate, systolic and diastolic blood pressure. Cognitive performance will be assessed with the Stroop test, mathematical processing test (MPT), and continuous performance test (CPT). Nicotine withdrawal measures will be measured with the Nicotine Withdrawal Symptom Checklist (NWSC) and the Brief Questionnaire on Smoking Urges (BQSU).

B. Dose Finding Study

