Determination of the menthol doses: Once a subject completed the testing, a grand log-means of the intensity ratings were used to determine the menthol test concentration that best matched the overall intensity of the popular commercial product. This was determined to be the high dose of menthol. The low dose was determined as the menthol concentration at which subjects could discriminate effects vs. the no menthol control condition, but at which clear differences in ratings were observed as compared to a

[Type text]

[Type text]

clustering of responses (response plateau) at higher menthol concentrations. In addition to these studies, [name] laboratory analyzed the concentrations of menthol in the commercially available mentholated e-cigarette solution (about 35 mg/cc). Based on these findings, we chose two menthol doses that will be used in our study. While the high dose will have the same concentrations of menthol in mentholated e-cigarette solution (AmericaneLiquidStoreTM), the low dose will be minimally recognizable by participants as menthol flavor (about 5 mg/cc).

Potential additional learning from sensory testing: In addition to establishing menthol concentrations for clinical testing, the psychophysical data will also enable preliminary evaluation of potential sex and/or race differences in sensory and hedonic responses to menthol. The discovery of such differences would yield novel data on how inhaled menthol is perceived differently between these groups, and how these differences might contribute to variations in the enhancing effects of menthol on nicotine reinforcement.

C. Medical Monitoring and Safety

Subjects will be given a thorough physical examination prior to entry in the study. A physician will be present at all test sessions. Subjects will be attached to blood pressure and heart rate monitoring devices throughout each test session. An IV catheter will be in place throughout the session. Subjects will be administered nicotine only if the systolic blood pressure is <150 mmHg and heart rate <100 beats/minute. The subject's participation will be terminated if their blood pressure at any time is >170/110 mm Hg, the heart rate is >120 beats/min, or if the subjects develop signs and symptoms compatible with nicotine toxicity. Subjects will be monitored for two hours after the last nicotine administration.

D. Measures

a) Physiological:

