b) Menthol: USP grade natural menthol flavor (Flavor SavorTM) will be dissolved in the AmericaneLiquidStoreTM menthol e-cigarette solutions.. Menthol is widely used in a range of healthcare products and is classified by the FDA as compound that is Generally Recognized as Safe (GRAS). Menthol has mild anesthetic, antiseptic and counter irritant properties and is safe for oral ingestion, topical administration and inhalation.

- Menthol Administration: Participants will be instructed to take 6 inhalations, one inhalation every 15 seconds, for 90 seconds just prior to each nicotine / saline infusion (Vansickel *et al.* 2012). As described more fully below in the section Adaptation Session, subjects will be asked to use light, long inhalations of 3-4 seconds with vapor being pulled into the mouth initially then into the lungs at the end of the inhalation. The menthol / e-liquid base mixture used in the e-cigarette will be prepared just prior to each Test Session by the VA Research Pharmacy. Each e-cigarette cartridge will contain 2mL of the e-liquid. The cartridge will then be loaded into the e-cigarette device by the study physician.

[Type text]

[Type text]

- a. Justification for menthol doses: For this proposal, the concentrations of the high and low dose menthol solutions were determined in the dose-finding study. These concentrations were found to be different in overall sensory impact from the control flavor and from each other. The target concentrations for this study are 3.5% (35 mg/mL) and 0.5% (5 mg/mL). Human toxicity only occurs at concentrations well above those to be used in this study. The concentrations of menthol in the stock solutions procured from the AmericaneLiquidStore™ will be verified using an assay developed by [name].

F. Electronic Cigarette

- Hardware: The Joyetech eGo-C™ e-cigarette will be used since it appears to be among the most widely used e-cigarette type and allows for flexibility in the type of e-liquid administered.
- Ingredients: E-liquid will be obtained from AmericaneLiquidStore™, which prepares all its products in Wauwatosa, Wisconsin. They claim to be the first e-liquid manufacturer in the United States to obtain International Organization for Standardization (ISO) 9001:2008 and Current Good Manufacturing practices (cGMP) certification.

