In order to participate in a study, each subject must give informed consent. All potential risks will be described in detail to the subjects in the consent form. The personnel in the laboratory have been certified in either Advance Cardiac Life Support (ACLS) or Basic Life Support. If a problem arises, the subject will be treated immediately.

Confidentiality in this study is of the utmost importance to us. All information obtained will be stored in coded form. The names of the subjects will be used in hospital records.

The risk associated with participating in this study is moderate, because the nicotine administered may be associated with mild side effects. Serious side effects associated with this treatment are not expected. This project will be monitored by the Center's Data and Safety Monitoring Board (DSMB) because the study involves double-blind treatment of smokers with nicotine. This board is composed of persons not otherwise affiliated with the clinical study who are experienced in various aspects of the conduct of clinical trials for the treatment of addictive disorders. The Yale TCORS Independent Data Safety Monitoring Board includes experts in the field of tobacco use behaviors and challenge studies (Chair: [name], FRCPC, Professor and Co-Director, Division of Brain and Therapeutics, Dept. of Psychiatry, U of Toronto; [name], Professor and Chair, Department of Health Outcomes & Behavior, H. Lee Moffitt Cancer Center & Research Institute) and in statistics ([name], Assistant Professor of Neurobiology, Columbia University). The members of the DSMB, and all study Investigators, will complete Conflict of Interest forms created by Yale's IRB in accordance with NIH guidelines.

We will report recruitment, follow-up, and adverse events to this panel on a bi-annual basis with serious adverse events reported within 48 hours. Prior to study initiation, critical parameters for collection of side effects and for study discontinuation will be recommended to the DSMB who may use these or other measures to monitor safety of the ongoing trial. The DSMB will be available to convene outside of scheduled meetings, if necessary, due to concerns regarding a particular subject or due to any troublesome developments in subjects' experiences during the study. The DSMB will make appropriate recommendations for changes in the study protocol, if needed.

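### Menthol is at most partly masked for participants: limit the double-blind claim to the infusion and take the direction of hypothesis 1A from the change from saline

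*Protocol*

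**What the plan says.** - **Label.** Protocol section 11.A: "We are proposing a double-blind, placebo-controlled study that enrolls young adult smokers stratified for menthol preference". Nothing there limits the blind to one factor. Section 13, explaining why a monitoring board is used, is narrower: "because the study involves double-blind treatment of smokers with nicotine".
- **Low dose.** Section 11.B gives the rule: "The low dose was determined as the menthol concentration at which subjects could discriminate effects vs. the no menthol control condition". It was also to lie clearly below the plateau of ratings at higher concentrations. Section 11.A adds: "The low dose menthol solution contains menthol that is minimally perceptible by smokers".
- **High dose.** Section 11.B takes the concentration "that best matched the overall intensity of the popular commercial product".
- **Result.** Section 11.E, justification for menthol doses: "These concentrations were found to be different in overall sensory impact from the control flavor and from each other".
- **Exposure.** Each participant has three Test Sessions, with "a different menthol condition for each session". Each session contains one saline and two nicotine infusions. The Adaptation Session has already given every participant the control flavor alone.
- **Outcomes and decision rule.** Section 12 makes the good-effects and drug-liking items of the DEQ the main outcomes. Support for hypothesis 1A needs a significant nicotine × menthol interaction and a significantly higher response to menthol + nicotine than to control flavor + nicotine or control flavor + saline. Hypothesis 1B needs the three-way interaction with preference group, and stronger effects in menthol smokers.

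**The concern.** A reader takes an unqualified double-blind label to mean that comparisons between menthol conditions are protected from the participant's knowledge of what was inhaled. The protocol's own account of dose selection points the other way, and the participant is the rater. The groups are defined by liking menthol cigarettes or not, so recognizing the flavor is likely to move ratings of liking for reasons unrelated to nicotine. If that shift can supply the higher response that section 12 asks for, the trial could report enhanced nicotine reinforcement when it has measured flavor preference.

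**Working it through.** **1. Is menthol masked for participants?** The protocol states no blinding figure to reproduce, so the sections are set side by side.
- High dose versus control: 35 mg/mL against none, matched to a commercial menthol product and reported as different in sensory impact. Masking is not credible here.
- High versus low: 35/5 = 7 times the concentration, and reported as different.
- Low versus control: selected as discriminable, but called minimally perceptible. Some participants may not notice it.
- Cues: the control flavor is already known from the Adaptation Session, all three conditions are sampled in turn, and the DEQ asks about cooling and irritation.

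**2. Where does a flavor shift go?** Take mean ratings for one nicotine dose. Let N be the nicotine effect under control flavor, x the shift from flavor preference (equal under saline and nicotine), and k the amount by which menthol *reduces* the nicotine effect.
- Control flavor + saline: m
- Control flavor + nicotine: m + N
- Menthol + saline: m + x
- Menthol + nicotine: m + x + N − k

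The contrasts are then:
- Menthol + nicotine minus control flavor + nicotine = x − k. The shift enters in full.
- Menthol + nicotine minus control flavor + saline = x + N − k. The shift enters in full, together with the nicotine effect itself.
- (Nicotine minus saline under menthol) minus (nicotine minus saline under control flavor) = (N − k) − N = −k. The shift cancels.

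The interaction in section 12 is a test on a 3 × 3 layout with (3 − 1)(3 − 1) = 4 degrees of freedom. It has no sign. If 0 < k < x, the interaction is real, both simple contrasts are positive, and hypothesis 1A is met as worded, although menthol has *weakened* the nicotine effect. Hypothesis 1A also names menthol + saline as a comparator. That is the one comparator sharing the flavor, and the decision rule leaves it out.

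**3. How large could this be?** The documents give no value for x. For illustration, assume no true menthol effect, a two-sided paired t-test of the same-dose contrast, and a shift b in SDs of the paired difference. Power follows from the noncentral t with n − 1 degrees of freedom and noncentrality b√n. Section 12 gives 60 completers, 30 per group, and levels 0.05 and 0.01.

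| b (assumed) | n = 60, 0.05 | n = 60, 0.01 | n = 30, 0.05 |
|---|---|---|---|
| 0.1 | 11.9% | 3.5% | 8.3% |
| 0.2 | 33.2% | 14.2% | 18.5% |
| 0.3 | 62.8% | 37.6% | 35.5% |
| 0.5 | 96.8% | 88.2% | 75.4% |

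The n = 60 columns assume the same average shift in the pooled sample. If the two preference groups shift in opposite directions, the pooled shift is smaller and the n = 30 column applies within a group. These are rejection rates for the simple contrast only, not for the full rule for hypothesis 1A.

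**4. What does the cleaner contrast cost?** With variance s² per rating and one common correlation r, the simple contrast has variance 2s²(1 − r) and the difference of differences 4s²(1 − r). The standard error rises by √(4/2) = 1.41. If ratings within a session correlate at r_w and between sessions at r_b, the variance ratio is 2(1 − r_w)/(1 − r_b), so the loss is smaller when r_w exceeds r_b.

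**The case against.** The strongest defense is that section 12 does not accept the simple contrasts alone. The interaction is required too, an additive flavor shift cancels there, and an additive shift specific to each group cancels in the three-way test for hypothesis 1B. This stands and narrows the point considerably. It is incomplete because the interaction carries no direction, and for hypothesis 1A the direction is taken from the exposed contrasts.

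It can also be said that menthol's sensory effect is part of the exposure under study, so detectability is unavoidable, and that section 13 already ties the blind to nicotine. Both are fair. They argue for limiting the label in section 11.A, not for leaving it as it is.

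Three stronger readings are tempting and are not supported:
- A reader might infer that the physician is unblinded, since "The cartridge will then be loaded into the e-cigarette device by the study physician". The text does not say that the physician knows the content. The Research Pharmacy prepares the liquid, coding is not described either way, and recognition by smell would be inference.
- A reader might infer that every menthol condition is identifiable and no menthol contrast is masked. The doses were set from averaged ratings in a separate dose-finding study. In the trial, sessions are at least 24 hours apart in random order, with the same tobacco flavor throughout. Identification of the low dose by each participant is not shown. Nor were both doses chosen to be discriminable: the high dose was matched to a product.
- A reader might take the remark in section 6 that blinding is unfeasible as an admission about this design. It concerns direct comparison of menthol and non-menthol cigarettes, the difficulty this design sets out to avoid.

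**Conclusion.** The point holds in limited form. By the protocol's own account, participants are at most partly masked to menthol: clearly not for high dose versus control, and doubtfully for low dose versus control. The infusion blind is untouched, and nothing shows staff unblinding. The consequence lies in the decision rule. A flavor-preference shift of x mm on the 100 mm scale enters both simple contrasts in full and can supply the higher response required by hypothesis 1A without any gain in nicotine reinforcement. The size of x is unknown, and the rejection rates above rest on assumed shifts. The interaction protects only against a shift that is equal under saline and nicotine. On a bounded scale a floor under saline could break that equality, but the documents offer no evidence either way.

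**What to change.** 1. **Section 11.A:** limit double-blind to the intravenous infusion, in line with section 13, and state that menthol is at most partly masked for participants because the conditions differ perceptibly.
2. **Section 12, hypothesis 1A:** keep the interaction test, but take its direction from the within-session change from saline: (nicotine minus saline under menthol) minus (nicotine minus saline under control flavor), required to be positive. With two nicotine and two menthol doses there are four such contrasts, to be covered by the Bonferroni correction already planned for post-hoc tests. State that same-dose contrasts between menthol conditions do not by themselves show enhanced nicotine reinforcement.
3. **Section 12, hypothesis 1B:** compare the same contrast between menthol and non-menthol smokers.

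The cost is wording and a less precise contrast: a standard error 1.41 times larger under equal correlations, less if ratings within a session agree more closely than ratings between sessions. Every session already includes saline, so no data are added. The change does not remove expectancy that differs between saline and nicotine.

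Optional: state that cartridges are coded, or have the pharmacy load the devices, and add one end-of-session item asking which flavor was given, reported by preference group.

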- b) Test Sessions: Experimental sessions will start around 8:30 AM. As summarized in Table 2, baseline biochemical measures will include urine menthol glucuronide and cotinine, plasma nicotine, and for women, estradiol and progesterone levels. These samples will be obtained followed by cognitive testing. Subjects will then start inhaling from the e-cigarette with the assigned menthol condition (control flavor, low or high dose of menthol), one inhalation every 15 seconds as practiced in the adaptation session. It will take approximately 90 seconds to complete 6 inhalations. Subjects will then receive the first delivery of the assigned injection (saline, 0.25 mg/70 kg or 0.5 mg/70 kg nicotine). Each study injection will be 60 minutes apart to provide sufficient time for the physiological and subjective nicotine effects to return to baseline. Following each injection, physiological, subjective, and cognitive outcome measures will be obtained.
- c) Medical monitoring: For nicotine test sessions, a physician will be present and subjects will be attached to a blood pressure and heart rate monitoring device. An IV catheter will be in place throughout the session. Subjects will be administered nicotine only if the systolic blood pressure is <150 mmHg and heart rate is <100 beats/minute. Subjects will be terminated from the study if the blood pressure at any time is >170/110 mm Hg, the heart rate is >120 beats/min, or if they develop signs and symptoms compatible with nicotine toxicity. Subjects

[Type text]

[Type text]

will remain in the laboratory for three hours after the last nicotine administration. These procedures have been developed as part of our IND application for IV nicotine.

Table 2. Schedule of Events: Experimental Session*

Time	Measures and Events
8:00 AM	(Building 36) CO level, urine sample, BAL, and light standard breakfast
9:00 AM	(Biostudies Unit) blood sample. HR/BP, EKG, M-NWSC, BQSU, SAFTEE, Cognitive Testing
11:00 AM	Menthol (control, high or low Menthol) DEQ + IV Saline or Nicotine (0.25 or 0.5mg/70 kg) blood draw
11:01	HR/BP, DEQ
11:02	HR/BP
11:03	HR/BP, DEQ,
11:05	HR/BP, DEQ
11:08	HR/BP, DEQ blood draw
11:10	HR/BP, DEQ
11:15	HR/BP, DEQ, Cognitive Testing
11:30	HR/BP, DEQ blood draw
11:45	HR/BP, DEQ
11:55	HR/BP, DEQ, BQSU
12:00	Menthol (control, high or low Menthol) DEQ + IV Saline or Nicotine (0.25 or 0.5 mg/70 kg), blood draw
13:00	Menthol (control, high or low Menthol) DEQ + IV Saline or Nicotine (0.25 or 0.5 mg/70 kg), blood draw

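### The pre-infusion dosing criterion limits systolic pressure and heart rate but has no diastolic term, although diastolic pressure above 110 mmHg ends participation

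*Protocol*

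**What the plan says.** The dosing criterion appears twice in the Protocol, with the same content. Section 11.C (Medical Monitoring and Safety) has: "Subjects will be administered nicotine only if the systolic blood pressure is <150 mmHg and heart rate <100 beats/minute". Study Procedures, item c) Medical monitoring, repeats it: "Subjects will be administered nicotine only if the systolic blood pressure is <150 mmHg and heart rate is <100 beats/minute".

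Each is followed by a termination rule. In 11.C: "participation will be terminated if their blood pressure at any time is >170/110 mm Hg, the heart rate is >120 beats/min". In Study Procedures: "Subjects will be terminated from the study if the blood pressure at any time is >170/110 mm Hg, the heart rate is >120 beats/min". Signs of nicotine toxicity also end participation in both places.

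Diastolic pressure is already among the planned measurements (11.A Overview): "Cardiovascular measures include heart rate, systolic and diastolic blood pressure". On the origin of the rules, Study Procedures adds: "These procedures have been developed as part of our IND application for IV nicotine".

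**The concern.** Three quantities can end a subject's participation: systolic pressure, diastolic pressure and heart rate. For two of them the protocol sets a lower value that must be met before nicotine is given, so a subject close to a stopping limit is not dosed. For diastolic pressure there is no such value.

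This matters because nicotine is expected to push these quantities upward. The Protocol names raised heart rate and blood pressure as common side effects (11.E Drugs; section 13, Potential risks). A subject dosed at diastolic 110 mmHg crosses the stopping limit with any further rise. The criterion is also one that gets used: section 13 (Protection of Subjects) counts raised pressure before dosing among the commonest adverse events or reasons for discharge in the group's previous IV nicotine studies. At stake is subject safety, and consistency between physicians in a repeated decision. Test of the study hypotheses is not at stake.

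**Working it through.** **Inputs.** Dosing criterion: systolic <150 mmHg and heart rate <100/min. Termination: blood pressure >170/110 mmHg or heart rate >120/min. Both come from 11.C and from Study Procedures c), which agree.

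**Margin = termination limit minus dosing limit.**

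| Quantity | Dosing limit | Termination limit | Margin |
|---|---|---|---|
| Systolic (mmHg) | 150 | 170 | 170 − 150 = 20 |
| Heart rate (/min) | 100 | 120 | 120 − 100 = 20 |
| Diastolic (mmHg) | none | 110 | at worst 110 − 110 = 0 |

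**Test case: 148/110 mmHg, heart rate 95.**
- Dosing criterion: 148 < 150 and 95 < 100, so it is met.
- Termination: 148 is not > 170, 110 is not > 110 (the inequality is strict), and 95 is not > 120, so it is not triggered.
- Result: the written rules do not bar the infusion. At 148/111 termination would apply, because 111 > 110. The highest diastolic value left open is therefore 110 itself.

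**How >170/110 is read.** The table takes it in the usual sense, that either component is enough. If both had to be exceeded, diastolic pressure would have no ceiling at all while systolic stays below 150. The check uses the reading more favourable to the protocol. The text does not say in words which one applies.

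**Whether another section closes the gap.**
- Section 7 requires good health and lets the physician exclude major illness, with no blood-pressure figure.
- Section 9 lists a physical examination, with no figure.
- Section 13 says subjects are screened for high blood pressure, again with no figure, and screening does not govern pressure at the time of infusion. For stopping rules it refers back to Study Procedures.
- No numeric diastolic limit for entry or dosing was found.

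**How often the criterion applies.** Section 11.A: "In each Test Session, smokers will receive a random order of one intravenous delivery of saline, and two intravenous deliveries of nicotine". With three sessions, a completer has 3 × 2 = 6 nicotine infusions among 3 × 3 = 9 infusions. The documents give no frequency for high diastolic pressure with acceptable systolic pressure and heart rate, so the number of infusions in the gap cannot be estimated.

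**The case against.** The strongest reply is that the rule is a necessary condition. It says when nicotine may not be given; it does not direct dosing whenever its two conditions are met. A physician attends every session with monitors attached and may withhold. Termination applies at any time, so on the either-component reading nobody above 110 mmHg is dosed. All of this stands. A reader might infer that the protocol instructs staff to infuse at 148/110; the text does not support that, only that nothing written prevents it.

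Second, subjects are healthy and aged 18 to 30, doses are capped at 0.3 and 0.6 mg, and the group reports more than 400 smokers given IV nicotine without an adverse event attributed to it. This also stands and keeps the severity low.

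Third, the protocol states no principle of a 20-unit buffer. The two equal differences are an observation, in different units, and do not oblige the sponsor to use 90 mmHg (110 − 20). The IND, which is not available here, may hold a diastolic value or a reason for omitting one. Fair, but if a value exists there, the protocol that staff work from should carry it.

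Fourth, physician discretion might be thought to make a number unnecessary. That does not stand: the protocol chose numbers for the other two quantities with the same physician present.

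A reader might also infer that a diastolic criterion would cost exactly one infusion and spare the subject a discharge. The protocol does not say whether a failed criterion means skipping, delaying, rescheduling or discharging, so neither half of that can be claimed.

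**Conclusion.** The concern holds as an incomplete safety rule, stated the same way in two places. Systolic pressure and heart rate each have a 20-unit margin between dosing and termination; diastolic pressure has none, and values up to and including 110 mmHg are not barred by the written rules. This rests on reading >170/110 as either component and on the absence of a numeric diastolic limit elsewhere in the Protocol. It does not show that any subject would in fact be dosed at such a value.

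Practical risk is small. The primary analysis method for the Drug Effects Questionnaire and its alpha are unchanged. Cheap improvement, patient safety, low severity.

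**What to change.** In 11.C and in Study Procedures c), add a diastolic criterion below 110 mmHg to the dosing rule, for example: and diastolic <100 mmHg. The responsible physician should set the final value consistent with the IND; the documents supply none, and <100 is only an example (it leaves 110 − 100 = 10 mmHg). In the same two places, state that >170/110 means systolic >170 or diastolic >110.

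The cost is a wording amendment in two places, checked against the IND, with no new measurement. The downside is that a nicotine infusion will occasionally not be given on diastolic grounds. Because the protocol does not say what follows a failed criterion, the resulting data loss cannot be quantified from the documents.
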